### 7.2 Statistical Analyses

#### 7.2.1 Hypotheses:

H1: SHI or pulse inversion HI will improve the diagnostic accuracy of mammography, grayscale US or power Doppler imaging to distinguish benign from malignant breast disease. The fundamental hypothesis is that the area under the ROC curve will improve by 0.10 to 0.15 with SHI compared to the other imaging modalities.

H2: Some findings of SHI (including perfusion estimates and CMI-SHI) or pulse inversion HI correlate with the pathological diagnosis of benign/malignant or with other significant physiological/pathological parameters. The fundamental hypothesis is that higher correlation coefficients can be achieved with SHI than with pulse inversion HI.

H3: 3D SHI estimates of perfusion correlate with absolute perfusion measured in the kidneys of dogs. The fundamental hypothesis is that correlation coefficients above 0.75 can be achieved for *in vivo* SHI perfusion estimates.

H4: *In vivo* fractional tumor vascularity measurements obtained with power Doppler imaging, pulse inversion HI or SHI correlate with iMVD or any other pathological measure of breast tumor vascularity obtained in the surgical biopsy specimens. The fundamental hypothesis is that higher correlation coefficients can be achieved with SHI than with the other two US flow modes.

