### 7.2.2 Analysis of Results

The findings of SHI, pulse inversion HI and PDI will be correlated to vascular morphology (i.e., tumor angiogenesis) and other pathological findings; including a) size b) vascularity, and c) type of mass. For cancers, pathological criteria, which will be evaluated, are the stage of the cancer, degree of proliferation and presence or absence of receptors. For the pre and post-contrast enhanced comparisons, dichotomous parameters (e.g., benign/malignant) and ranked data (less, iso, or more intense) will be analyzed with the McNemar test which measures significance of changes in related samples (pairwise comparisons). For variables in which accurate numerical measurement is possible (e.g., perfusion), the techniques will be compared using an ANOVA.

The ability of the imaging tests to distinguish benign from malignant masses will be compared using ROC analysis, while the incremental validity of imaging diagnosis and mammography will be analyzed using logistic regression and ROC analyses [DeLong et al. 1988; Metz 1986; Wagner et al. 2001]. The tests are: x-ray mammography, fundamental grayscale US imaging, PDI, pulse inversion HI and SHI (as well as SHI with CMI-SHI added), while pathology (based on excisional or core biopsies) will provide the reference standard. All studies will be rated on a quasi-continuous scale from 0 to 100, since this has an intuitive probabilistic interpretation and improves the assessment of the characterization capabilities of the imaging modalities compared to using a coarser 6-point scale [Wagner 2001]. Logistical regression techniques will be used to combine the 4 US imaging modes and mammography as well as to incorporate the quantitative parameters into the SHI diagnosis before repeating the ROC analysis. This will allow all possible combinations to be compared to one another (e.g., mammography versus all the US modes combined or mammography and grayscale US versus mammography and grayscale US and SHI, etc.). Differences between ROC curves will be tested by computing Mann-Whitney statistics.

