All histopathological variables will be compared to imaging judgments on diagnoses and characteristics of vascularity for the different modalities. When both sets of variables are nominal, chi-square tests will be conducted. When both types of variables are ordinal or continuous, correlations will be calculated. When one type of variable is nominal and one continuous non-parametric rank order tests such as Mann-Whitney U-tests or Kruskal-Wallis tests will be performed [Rosner 1990]. Inter- and intra-observer variability will also be determined by calculating the intraclass correlation coefficient and the kappa statistic [Shrout 1979; McGraw 1996].

Comparisons of sensitivities, specificities and accuracies for diagnosing cancer with the different imaging modalities will be conducted with McNemar's test for correlated proportions (against the histopathological gold standard). All of the statistical analyses proposed for the human clinical trial will be repeated split by racial and ethnic groups to determine if clinically important race/ethnicity differences exist in the ability of 3D SHI to diagnose breast cancer.

Finally, the vascularity measures obtained from the subgroup of up to 85 CD31 stained breast tumor specimens will be compared to the fractional tumor neovascularity data to determine if any correlation exists (in baseline PDI or one of the two contrast enhanced modes). The existence of a linear relationship between ultrasonic and pathologic data will be assessed using single variable linear regression techniques and reverse stepwise multiple linear regression analysis.

All analyses and computations will be performed using NCSS/PASS 2005 and Stata 9.0 (Stata Corporation, College Station, TX), while the study database will be designed and implemented in Filemaker Pro 10.0 (Filemaker Inc, Santa Clara, CA). This database will contain all patient information (except names and other identifiers), including the answers to the questionnaire, and the results of the various US imaging modes as well as the pathology results.

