#### 7.2.4 Sample Size Calculation

A power analysis was performed using NCSS/PASS 2005 (NCSS, East Kaysville, UT) to estimate the number of cases required in the positive and the negative group (i.e., the malignant and benign cases, respectively) to achieve significance at the 0.05 level (on a two-sided test) when comparing binormal ROC curves (i.e., for specific aim 3) based on the primary reader ([name]) reading all cases.

For this study to demonstrate that 3D SHI produces a 10 % increase in diagnostic accuracy with 90 % statistical power requires between 400 and 600 patients (depending on the positive biopsy rate). If the real increase in accuracy is 15 %, then between 167 and 300 cases are needed to achieve 90 % power. Consequently, we selected a sample size of 450 patients for this clinical trial, which will allow us to detect a 15 % increase in the diagnostic accuracy of diagnosing breast cancer with over 90 % statistical power (assuming a positive biopsy rate of around 20 %). If the actual positive biopsy rate is approximately 30 %, then we will have more 90 % power to detect a 10 % increase in accuracy.

For Hypothesis # 3, we assumed that the correlation coefficient achievable with 3D SHI perfusion estimates will be 0.75 whereas our preliminary work with 2D SHI achieved a coefficient of 0.57 [Forsberg et al. 2006a]. This difference will be detectable with more than 80 % power at the 0.05 significance level (on a two-sided test) when 152 data points are analyzed. Hence, the decision to study 5 dogs for a total of 160 perfusion estimates. Finally, for Hypothesis # 4, we assumed that the correlation coefficient between power Doppler imaging and pathology will be approximately 0.40 (since our preliminary work [Caudhari et al. 2000; Forsberg et al. 2008] achieved coefficients between 0.25 and 0.49). Then we will have more than 80 % power to detect an improvement in the correlation by 0.3 or more due to SHI at the 0.05 significance level (using a two-sided test) when 84 patients are analyzed.

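### The plan sets out to determine whether SHI performs differently across racial and ethnic groups, but names no comparison between groups and no rule for judging a difference

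*Combined protocol and SAP*

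**What the plan says.** Section 7.2.2 (Analysis of Results) states that every analysis of the human trial "will be repeated split by racial and ethnic groups to determine if clinically important race/ethnicity differences exist". The same sentence gives the purpose in full: "to determine if clinically important race/ethnicity differences exist in the ability of 3D SHI to diagnose breast cancer".

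The analyses to be repeated are all in Section 7.2.2:

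- ROC comparison of the imaging tests: "Differences between ROC curves will be tested by computing Mann-Whitney statistics".
- Sensitivity, specificity and accuracy: comparisons between modalities "will be conducted with McNemar's test for correlated proportions (against the histopathological gold standard").
- ANOVA to compare techniques on numerical measures; chi-square, correlation and rank tests relating imaging to pathology; intraclass correlation and kappa for the readers.
- Logistic models: "Logistical regression techniques will be used to combine the 4 US imaging modes and mammography", and to bring the quantitative parameters into the SHI diagnosis. No term for race or ethnicity is mentioned.

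The plan does not list the groups, give a minimum size or pooling rule, define a clinically important difference, or name an interaction or heterogeneity test. Race and ethnicity do not appear in the objectives (Section 2) or in H1 to H4 (Section 7.2.1). The sample size in Section 7.2.4 covers the cohort as a whole.

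**The concern.** The purpose is a question about a difference between groups. The named tools answer another question, asked once per group: does one imaging mode beat another here, or does imaging track pathology here? Whether such a test reaches significance depends heavily on how many cancers the group contains. A pattern of success in one group and failure in another can therefore arise with the same true gain in both. Setting the group AUCs side by side by eye is no better calibrated unless the difference between them carries an interval.

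At stake is a report that SHI helps women of one racial or ethnic group and not another when nothing of the kind is true. Equally, a real difference would have no agreed way of being shown.

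**Working it through.** **The plan's own figures.** No power is stated for the race/ethnicity question. For the whole cohort, Section 7.2.4 claims over 90% power for a 15% gain with 450 patients and 20% malignant. A binormal variance for two correlated AUCs, with base AUC varied over 0.64–0.80 and correlation over 0–0.6, gives at least 0.90 in every variant, which agrees. The stated ranges (400–600 patients for a 10% gain, 167–300 for 15%) are plausible, but cannot be reproduced exactly because neither base AUC nor correlation is given.

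Those ranges already show the difficulty. Two groups sharing 450 women cannot both reach 400, and the smaller has at most 225. At 80/20 it has 90 women (18 cancers at the 20% rate). At 90/10 it has 45 (9 cancers). Both fall well below 167.

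**Inputs.** From the documents:

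- N = 450, with 20% or 30% malignant (Section 7.2.4).
- The test level: "to achieve significance at the 0.05 level (on a two-sided test").
- The effect: "the area under the ROC curve will improve by 0.10 to 0.15 with SHI" (Section 7.2.1, H1).

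Assumed, because the documents do not say:

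- Two groups, split 50/50, 80/20 or 90/10, with the same malignant share and the same true gain in each.
- Base AUC 0.67–0.75, guided by the pilot values 0.64, 0.67 and 0.76 in Section 1.1.
- Between-mode correlation 0.3, with 0.5 as a variant.

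**One case by hand** (80/20, 20% malignant, AUC 0.67 to 0.77, correlation 0.3). The simulated standard errors of the gain are 0.040 (n = 360) and 0.077 (n = 90). Power is approximately Φ(gain/SE − 1.96):

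- Larger group: Φ(0.10/0.040 − 1.96) = Φ(0.54) ≈ 0.70; simulated 0.69.
- Smaller group: Φ(0.10/0.077 − 1.96) = Φ(−0.66) ≈ 0.25; simulated 0.255.
- Larger significant and smaller not: 0.69 × (1 − 0.255) = 0.51.
- SE of the difference in gains: √(0.040² + 0.077²) = 0.087, so the 95% half-width is 1.96 × 0.087 = 0.17.

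**All cases** (simulation with DeLong variances, identical true gain in both groups):

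| Split | Outcome counted | Correlation 0.3 | Correlation 0.5 |
|---|---|---|---|
| 80/20 | larger significant, smaller not | 25–60% | 17–61% |
| 90/10 | larger significant, smaller not | 55–75% | 44–76% |
| 50/50 | groups disagree, either direction | 2–25% (gain 0.15); 40–50% (gain 0.10) | 0–52% (both gains) |

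With 500 trials per cell the simulation error is about √(0.5 × 0.5/500) = 2 points. The 50/50 entry for a 0.10 gain was 42–49% at that size and 38–50% with 2,000 trials per cell, so it is rounded here. With 2,000 trials the other ranges were 25–58%, 55–75% and 2–23% at correlation 0.3, and 15–58%, 46–75% and 0–47% at 0.5.

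**The direct comparison.** Take z = (gain₁ − gain₂)/√(SE₁² + SE₂²). With identical gains its false-positive rate was about 4–9% across these cases. The 95% half-width at 80/20 and correlation 0.3 is about 0.13–0.18. For true gains of 0.15 and 0.05, its power by formula (base AUC 0.70–0.78, correlation 0.3–0.5) is about 27–45% at 50/50 and 12–19% at 90/10. The smallest difference detectable with 80% power is about 0.15–0.21 at 50/50 and 0.26–0.36 at 90/10.

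**The case against.** A reader might infer that the plan commits the trial to declaring a racial difference whenever one group is significant and another is not. The documents do not support that. Nowhere do they say that group p-values will be compared. The repeated analyses also yield AUCs, sensitivities and specificities that can be set side by side, and the stated interest in clinical importance points to size rather than significance. What can be said is narrower: no between-group comparison is named, and the rule for judging is left open.

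A reader might also infer that the trial's main result is compromised. It is not. This is one sentence on a question outside the objectives and H1 to H4, and the whole-cohort ROC comparison does not depend on it.

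The percentages rest on a group mix, base AUC and correlation that the documents do not give. With an even split and a 0.15 gain, disagreement can almost vanish. That is fair, and is why the 50/50 row is shown. For a 0.10 gain, however, it stays at about 25–50% even at 50/50 across both correlations.

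Finally, a direct test would have low power. That is true, and it argues for an interval and an exploratory label, not for leaving the comparison out.

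**Conclusion.** The point holds as a gap in the plan: Section 7.2.2 promises to determine whether groups differ, and supplies only analyses that never set one group against another. The harm is conditional. If within-group significance fills the gap, a false appearance of difference is common when groups are unequal (roughly a quarter to three fifths of trials at 80/20, more than half at 90/10). It ranges from rare to about one in two when they are equal. These sizes assume two groups with the same malignant share, base AUC 0.67–0.75 and correlation 0.3; at correlation 0.5 the lower ends fall but the conclusion does not change. At N = 450 the trial can estimate a between-group difference only imprecisely.

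**What to change.** Amend the sentence in Section 7.2.2 as follows:

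- Name the racial and ethnic groups, say how small ones will be pooled, and state what size of difference counts as clinically important.
- Keep the split as description: AUC, sensitivity and specificity per group with 95% intervals, alongside benign and malignant counts.
- Judge differences only by the between-group difference in AUC gain with its 95% interval, by z-test or bootstrap. Use one heterogeneity test if there are more than two groups.
- In the logistic models, add a rating-by-group interaction. The outcome there is malignancy and the modes enter as ratings, so the relevant term is the SHI rating crossed with group.
- Draw no conclusion from within-group p-values, and label the whole analysis exploratory.

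This needs no extra patients or readings, and Section 6.2 already has a full demographic profile recorded. The cost is a little more analysis and a visibly wide interval, which is an accurate picture of what 450 women can show.

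### H4 says SHI correlates better with pathological vascularity than PDI and pulse inversion HI, but no planned analysis tests one correlation against another, and SHI versus HI has no power basis

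*Combined protocol and SAP*

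**What the plan says.** Section 7.2.1 states H4 in two layers. The first is that fractional vascularity from PDI, pulse inversion HI or SHI will "correlate with iMVD or any other pathological measure of breast tumor vascularity". The second, called the fundamental hypothesis, is comparative: "higher correlation coefficients can be achieved with SHI than with the other two US flow modes". H2 makes a similar comparative claim: "higher correlation coefficients can be achieved with SHI than with pulse inversion HI".

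Section 7.2.4 treats H4 as a formal comparison. It assumes a PDI correlation with pathology of about 0.40 (preliminary values 0.25 to 0.49) and claims more than 80% power, two-sided at 0.05, for an improvement of 0.3 due to SHI in 84 patients. It gives no correlation for HI.

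Section 7.2.2 sets the H4 analysis on up to 85 CD31-stained specimens. Its purpose is "to determine if any correlation exists (in baseline PDI or one of the two contrast enhanced modes"), and the linear relationship is to be "assessed using single variable linear regression techniques and reverse stepwise multiple linear regression analysis". The general rule earlier in that section is: "When both types of variables are ordinal or continuous, correlations will be calculated".

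**The concern.** The hypothesis and its sample size are about a difference between correlations. The analysis is about whether each correlation is non-zero. A single-variable regression tests one slope against zero, and stepwise selection reports which predictors survive. Neither gives an estimate, an interval or a test for r(SHI) minus r(PDI), or for r(SHI) minus r(HI).

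The three modes are measured in the same patients against the same specimen, so the correlations are dependent and need a paired test. H4 also leaves the pathology measure open, so the comparison could be made on whichever measure favours SHI.

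As written, the trial could finish with three coefficients, SHI the largest, and no rule for deciding whether that supports H4. For the HI half, nobody could say beforehand whether 84 patients were enough.

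**Working it through.** **1. Does any other planned method test the difference?** These are the between-mode methods in section 7.2.2:

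- McNemar compares paired proportions and ranked categories.
- For numerical measurements, "the techniques will be compared using an ANOVA". That compares the measured values of the modes, not how closely each tracks pathology.
- "Differences between ROC curves will be tested by computing Mann-Whitney statistics". That compares areas under ROC curves.

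None compares two correlation coefficients. For H2, the benign/malignant part is served by the ROC and McNemar comparisons. The gap there is confined to ordinal or continuous pathology parameters.

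**2. The plan's own figure.** Inputs from section 7.2.4: 0.40 (PDI), 0.40 + 0.30 = 0.70 (SHI), n = 84, two-sided 0.05. Fisher z for two independent groups:

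power = Φ( [atanh(0.70) − atanh(0.40)] / √(1/81 + 1/81) − 1.960 )
= Φ( (0.8673 − 0.4236) / 0.1571 − 1.960 ) = Φ(0.863) = 80.6%.

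n for 80% power = 2 × [(1.960 + 0.842) / 0.4437]² + 3 = 82.8, so 83. The stated 84 reproduces. The H3 figure (0.57 versus 0.75, n = 152) gives 80.2% by the same formula, which suggests that this independent-groups formula was the one used.

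**3. SHI versus PDI with a paired test.** Steiger's test for two correlations r1 and r2 sharing one variable, with between-mode correlation r12 and m = (r1 + r2)/2:

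Z = [atanh(r2) − atanh(r1)] × √(n − 3) / √(2 − 2s), where s = ψ / (1 − m²)² and ψ = r12(1 − 2m²) − ½m²(1 − 2m² − r12²).

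Power by simulation from trivariate normal data, n = 84, 40,000 replicates per cell. The documents give no r12, so a range is shown. The partial correlation given pathology is (r12 − 0.40 × 0.70) / √[(1 − 0.16)(1 − 0.49)] = (r12 − 0.28) / 0.6545.

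| r12 | Partial r given pathology | Power, SHI 0.70 vs PDI 0.40 |
|---|---|---|
| 0 | −0.43 | 77% |
| 0.1 | −0.28 | 80% |
| 0.28 | 0 | 87% |
| 0.5 | 0.34 | 95% |

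Power falls below 80% only if the two modes are negatively related once pathology is held fixed, which is implausible. So 84 is adequate for this half. Williams' t agrees within 0.4 points, and type I error with equal correlations (0.40 or 0.60) is about 5%.

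**4. SHI versus HI.** Same test, SHI 0.70, n = 84. Every HI value is an assumption, because the plan gives none. Figures hold to about one percentage point.

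| HI correlation | r12 = 0.5 | r12 = 0.6 | r12 = 0.7 |
|---|---|---|---|
| 0.40 | 95% | 98% | 100% |
| 0.45 | 87% | 93% | 97% |
| 0.49 | 75% | 82% | 91% |
| 0.50 | 71% | 79% | 89% |
| 0.60 | 27% | 31% | 38% |

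The highest HI correlation that still leaves 80% power is about 0.47, 0.49 and 0.52 at the three r12 values.

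**5. Both halves together.** H4 names both other modes. With PDI at 0.40 and (PDI–SHI, HI–SHI, PDI–HI) between-mode correlations of (0.28, 0.5, 0.3), (0.4, 0.6, 0.4) and (0.5, 0.7, 0.5), the chance that both tests are significant in favour of SHI is 66%, 75% and 86% if HI is 0.50. It is 26%, 30% and 37% if HI is 0.60.

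**6. What the planned output shows when there is no difference.** Let all three modes correlate 0.40 with pathology. SHI then has the largest coefficient in one study in three, by symmetry. With backward stepwise at 0.05 to stay (an assumption; the plan gives no threshold), SHI is the only mode kept in 3%, 15% or 30% of studies at equal between-mode correlations of 0.3, 0.5 or 0.7.

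**The case against.** The strongest reply is that section 7.2.4 already fixes the SHI-versus-PDI contrast, the alpha, the sidedness and the sample size, so only the name of the test is missing. The stated secondary aim compares SHI with pathology and does not mention superiority over other modes. H4 rests on a single-site subset, and a secondary contrast may go unpowered. This limits the weight of the point but does not remove it: the analysis section gives a different purpose for these data, and H4 as worded still needs a comparison.

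A second reply is that HI values of 0.50 and 0.60 lie above the only range in the documents, 0.25 to 0.49, and that the titles of the two sources cited for that range refer to contrast-enhanced imaging. This is fair, and it is why the table includes 0.40 to 0.49. Within that range the HI comparison is mostly adequate, but not always: at a between-mode correlation of 0.3, HI at 0.45 gives 75% and HI at 0.49 gives 62%. The plan applies the range to PDI and says nothing about HI.

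Third, the one-in-three figure is simple symmetry, and the stepwise figures depend on an assumed threshold and on treating sole retention as a decision, which the plan never states. They illustrate the problem and do not carry the argument. Finally, fractional vascularity is a bounded proportion, so the normal-theory power figures are approximate. That is a reason to report a bootstrap interval beside the test.

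**Conclusion.** The concern holds. Followed as written, section 7.2.2 cannot support or refute the comparative claim in H4, nor the SHI-versus-HI claim in H2 for ordinal or continuous pathology parameters. The stated 84 is not an error and suffices for SHI 0.70 versus PDI 0.40 under a paired test.

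The SHI-versus-HI half has no stated power basis. Depending on the HI correlation, power runs from about 27% (HI 0.60) to near 100% (HI 0.40) at between-mode correlations of 0.5 to 0.7. These figures assume trivariate normal data, 84 patients with all three modes measured, and HI and between-mode correlations that the documents do not give.

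The primary ROC comparison and the benign/malignant comparisons are not affected. This should be corrected, but it does not threaten the trial's main question.

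**What to change.** In section 7.2.2, name one pathology measure for H4, for example iMVD on the CD31-stained specimens, and treat the others as descriptive. Then add text such as:

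> Correlations of fractional vascularity with this measure will be compared for SHI versus PDI and for SHI versus pulse inversion HI, in patients with all three modes measured, by a test for dependent correlations sharing one variable (Williams or Steiger), with a patient-level bootstrap 95% interval for each difference. H4 is met only if both differences favour SHI and both are significant at two-sided 0.05.

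Because both tests must succeed, alpha need not be split between them.

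For H2, use a patient-level bootstrap of the difference in rank correlations (SHI versus HI) for ordinal or continuous parameters only. Leave the benign/malignant part to the planned ROC and McNemar comparisons.

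In section 7.2.4, give H4 power for the paired test over a range of between-mode correlations. Either state an assumed HI correlation with its power, or say that SHI versus HI is not powered.

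The cost is a few lines of text and code, with no extra patients, images or stains. The sponsor gives up two things: the statement for SHI versus HI becomes less favourable, and other pathology measures can no longer be used to declare H4 met.

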In a subset of cases at TJU (approximately 85) staining will also be performed for an immunohistochemical predictor of tumor angiogenesis, specifically a monoclonal antibody against the PECAM endothelial cell marker (anti-CD31; Dako Corporation, Carpinteria, CA) in addition to the standard H&E staining described above. The PI, as part of previously NIH and DOD funded projects, has developed the necessary software for quantitative analysis of contrast enhanced US images and specimens stained with CD31 using a histomorphometry system based on an SMZ-10A microscope (magnification 100x; Nikon, Melville, NY) and ImagePro Plus software [Chaudhari et al. 2000; Forsberg et al. 2008]. Vessels will be identified in the digitized image by the presence of CD31 staining. ROIs around visible vessels will be defined for the ImagePro software. This labor-intensive task will be performed by a graduate student under the direct supervision of the PI. A pathologist will be available for consultation ([name]).

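### Whether an ultrasound-pathology relationship exists in the CD31 subset is judged by uncorrected single-variable and reverse stepwise regression: about 14–15% false positives for the three named flow modes, if terms are removed at p>0.05

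*Combined protocol and SAP*

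**What the plan says.** Section 6.7 (Pathology) sets up the subset: "In a subset of cases at TJU (approximately 85) staining will also be performed" for CD31. Section 7.2.2 then takes "the vascularity measures obtained from the subgroup of up to 85 CD31 stained breast tumor specimens" and compares them with the fractional vascularity measured by ultrasound, "to determine if any correlation exists (in baseline PDI or one of the two contrast enhanced modes". The method follows in the next sentence: whether the two sets of measurements are linearly related "will be assessed using single variable linear regression techniques and reverse stepwise multiple linear regression analysis".

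So the stated purpose is inferential (does a relationship exist?), and two tools are named for it, side by side. The documents do not give:
- the list or number of candidate terms;
- the threshold for removing a term;
- which side of the regression is the response;
- an overall test or validation of the selected model;
- any multiplicity adjustment for this step.

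Hypothesis 4 in section 7.2.1 leaves the pathological side open as well. The ultrasound measurements are to "correlate with iMVD or any other pathological measure of breast tumor vascularity obtained in the surgical biopsy specimens". Its fundamental hypothesis is a different question: whether SHI gives higher correlation coefficients than the other two flow modes. Section 7.2.4 powers that comparison on the assumption that "the correlation coefficient between power Doppler imaging and pathology will be approximately 0.40", with an improvement of 0.3, "at the 0.05 significance level (using a two-sided test) when 84 patients are analyzed".

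**The concern.** Backward elimination drops the weakest term until every remaining term passes the threshold. A surviving term is therefore significant because that is how it was chosen. Reading its p-value as a test of existence uses the selection rule as the evidence. The printed p-values, R-squared and coefficients of the final model take no account of the search.

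The single-variable regressions run alongside do not repair this. Three unadjusted tests at 0.05 also give three chances of a false finding.

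At stake is a claim, under the secondary aim, that ultrasound vascularity tracks pathological vascularity. The error rate of that claim would be well above the 5% a reader would assume. The candidates and the threshold are unstated, so both could also be settled after the data are seen.

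**Working it through.** **1. The plan's own figure.** Section 7.2.4 claims more than 80% power for correlations of 0.40 versus 0.70 with 84 patients, two-sided 0.05. Fisher's z for two independent correlations, 84 each:

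- atanh(0.70) − atanh(0.40) = 0.8673 − 0.4236 = 0.4437
- SE = √(1/81 + 1/81) = 0.1571
- power = Φ(0.4437/0.1571 − 1.96) = Φ(0.864) = 80.6%

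The claim reproduces. It concerns a difference in correlations, not the stepwise output.

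**2. Inputs for the existence question.**
- From the documents: n = 85; three flow modes (PDI, HI, SHI).
- Carried over from section 7.2.4: a level of 0.05.
- Assumed, because not stated: the three modes are the candidate terms; removal at p>0.05; a relationship is declared if at least one term is retained; correlation among candidates between 0 and 0.7.

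**3. Approximate check by formula.** With k independent tests at 0.05, the chance of at least one false positive is 1 − 0.95^k:
- k = 3: 1 − 0.857 = 14.3%
- k = 8: 1 − 0.663 = 33.7%

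**4. Simulation under no relationship.** There were 4,000 data sets per setting, n = 85, with equally correlated normal candidates and an unrelated normal response. Backward elimination removed the largest p until all were below 0.05. Monte Carlo standard error is about √(0.14 × 0.86/4000) = 0.5 points at 14% and 0.3 points at 5%.

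| Candidates | Correlation among them | Stepwise keeps ≥1 term | Any single-variable p<0.05 | Full-model F test |
|---|---|---|---|---|
| 3 | 0 | 14.5% | 14.5% | 5.1% |
| 3 | 0.3 | 14.0% | 13.1% | 4.6% |
| 3 | 0.5 | 13.5% | 12.0% | 4.5% |
| 3 | 0.7 | 13.7% | 10.2% | 4.9% |
| 8 | 0 | 34.6% | 33.9% | 5.1% |
| 8 | 0.7 | 39.3% | 18.8% | 5.1% |

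A repeat with 6,000 data sets gave 14.1–14.7% for stepwise with three candidates and 33.8–40.1% with eight. At correlation 0.7 with three candidates, its single-variable rate was 10.7%. Taking the runs together and allowing for simulation error, the three-mode rates are about 14–15% (stepwise) and 11–14% (single-variable). A further run with eight candidates gave 34–41%.

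**5. Sensitivity to the unstated threshold.** With removal at 0.10 instead, three candidates give 27–28%.

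**6. Splitting the excess.** At three modes, stepwise exceeds the single-variable tests by 14.5 − 14.5 = 0 points when the modes are uncorrelated, and by 13.7 − 10.2 = 3.5 points at correlation 0.7. Most of the gap from 5% to 14% is therefore ordinary unadjusted multiplicity. Stepwise selection does clearly worse only with many correlated candidates.

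**7. Adjusted single-variable tests.** Bonferroni at 0.05/3 gives 1 − (1 − 0.0167)^3 = 4.9% if the three tests are independent, and no more than 5% otherwise.

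**The case against.** The strongest reply is that little depends on this analysis. It is a secondary-aim analysis in a single-site subset, and the powered part of Hypothesis 4 is a difference in correlations that the stepwise model does not decide. That stands, and it limits the weight of the point.

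Second, a world with no relationship is far from the plan's premises. At r = 0.40 and n = 85, a single-variable test has power Φ(0.4236 × √82 − 1.96) = Φ(1.88), about 97%. This also stands as a statement of what the sponsor expects. But section 7.2.2 still poses existence as a question to be tested, and a test needs a known error rate.

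Third, section 7.2.2 does not say that one retained term amounts to declaring a relationship. True; that rule is assumed here. The plan offers no other rule.

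Two stronger readings are tempting, and the documents do not support either:
- *A false-positive rate of 41%.* That needs eight strongly correlated candidates. Only three modes can be counted from the text, so the higher figure is illustrative.
- *Stepwise regression would pick an arbitrary winner between HI and SHI and so decide Hypothesis 4.* If HI and SHI are made equally good, with PDI at 0.40, stepwise keeps one without the other in roughly 8–44% of data sets. That range depends on correlations the documents do not give. The full model has a similar problem (6–32%), because collinearity drives it. The planned single-variable regressions would show both modes significant in over 99% of such data sets. The ranking of modes is assigned to the difference in correlations.

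**Conclusion.** The point holds as a recommended change, not a critical flaw. Section 7.2.2 uses uncorrected single-variable regressions and reverse stepwise regression to decide whether a relationship exists, with nothing to control the error. For the three named modes and removal at p>0.05, the stepwise false-positive rate is about 14–15% and the single-variable rate about 11–14%, against about 5% for the overall F test of the full model. The figures assume n = 85, that candidate set, that threshold, and one pathological outcome. More candidates, a looser threshold or several outcomes would raise them. Replacing stepwise regression alone would leave most of the inflation, so the single-variable tests must be covered too. Neither the primary ROC analysis nor the powered comparison of correlations is affected.

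**What to change.** Change the wording of section 7.2.2 before any CD31 data are linked to imaging:

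- Name iMVD as the main outcome for the existence test. Fit one model with PDI, HI and SHI fractional vascularity as predictors, with no selection, and judge existence by the overall F test at two-sided 0.05 level equivalent, that is p<0.05 for the F statistic.
- Keep the three single-variable regressions to describe which modes relate to iMVD, adjusted by Bonferroni or Holm. They should not serve as a second route to declaring existence.
- Label stepwise results and all other pathological measures exploratory, without confirmatory p-values. If stepwise output is shown, state the candidate list and removal threshold in advance.
- State that the term surviving selection will not be used to rank modes, and that the comparison of SHI with PDI and HI rests on the planned difference in correlation coefficients.

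The cost is wording only, with no added patients or procedures. The model is less parsimonious, the single-variable thresholds are slightly stricter, and the existence test is narrowed to one of the pathological measures that Hypothesis 4 allows.
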